#### 4.5.2 Prior and Concomitant Medications

Medications will be mapped to their corresponding thesaurus terms (ATC Class and Preferred Term) according to the World Health Organization (WHO) Drug Dictionary, Version Mar2016. A summary of concomitant medications, sorted by ATC Class 2 and Preferred Term, will be provided. A listing of prior and concomitant medications will be presented, as well a listing of any prohibited medications used during the study.

#### 4.5.3 Physical Examination

The results of the physical exams will be presented in a listing. Clinically significant changes from Baseline will be documented as an AE.

#### 4.5.4 Vital Signs

Blood pressure and pulse will be summarized from Baseline through Week 40/ET. Additionally, change from Baseline in vital signs will be summarized at Week 4, 12, 24, 36, and 40/ET. Clinically significant changes from Baseline will be documented as an AE.

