1.5 SUMMARY OF BENEFITS AND RISKS

The pathogenesis of acne vulgaris includes several mechanisms which are potential targets for nitric oxide. Nitric oxide has been demonstrated to inhibit several inflammatory pathways relevant in acne, decrease *P. acnes*, and decrease sebum production. In two completed Phase 2 studies, SB204 4% administered in subjects with acne decreased inflammatory and non-inflammatory lesion counts at the end of treatment and improved IGA scores. Once daily treatment was as effective as twice daily treatment. In the studies conducted to date, the systemic AE profile was similar between subjects treated with NVN1000 Gel, SB204, and subjects treated with Vehicle Gel. SB204 4% has been generally well tolerated and has not been associated with a safety or tolerability signal. In PK studies, there was no detectable systemic exposure to the parent compound, NVN1000, or changes in plasma nitrate.

Dermal toxicology studies in mice and minipigs have demonstrated minimal evidence of toxicity with mild-moderate dermal changes most frequently reported. In reproductive toxicology studies, findings were limited to toxicities associated with high methemoglobinemia at supra-therapeutic doses.

Based on the known mechanism of action of nitric oxide, theoretical risks from systemic exposure following topical administration of NVN1000 Gel or SB204 include hypotension and headache. Methemoglobin has been monitored in previous clinical studies with NVN1000 Gel and SB204 and no significant changes in methemoglobin levels have been observed.

Inadvertent administration to the eyes may result in ocular irritation due to the excipients and should be avoided. Should the product be accidently instilled in the eye(s), prompt flushing with copious amount of normal saline or water is recommended.

A transient (approximately 5-10 minutes), asymptomatic erythema has been observed in some subjects shortly after application of NVN1000 Gel or SB204 which is a physiologic response (vasodilation) to local nitric oxide release. Topical application has been associated with local application-site reactions including erythema, scaling, dryness, and burning/stinging. These local

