4.3.3 VITAL SIGNS

Blood pressure and pulse rate will be collected at Weeks 4, 12, 24, 36 and 40/ET. Any clinically significant changes in vital signs from Baseline will be recorded as adverse events whether or not drug related.

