#### 2.1 Safety Endpoints

Safety endpoints will include adverse events, changes in physical examination and changes in vital sign measurements. Any clinically significant changes noted during the physical exam as well as from the vital sign measurements will be recorded as adverse events and included in the comparison. Urine pregnancy tests in women of child-bearing potential will be conducted at each visit.

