## 4 Statistical Methodology

#### 4.1 Planned Analyses

All statistical processing will be performed using statistical analysis software (SAS®) unless otherwise stated. Safety analyses will be performed using the safety population.

Continuous data will be summarized with sample size (N), mean, median, standard deviation, minimum and maximum. Categorical data will be summarized with N, frequency counts, and percentages, based on N.

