#### <Parameter> (<units>)

	-	SB204
		N=XXX)
Timepoint	Actual	Change from Baseline
Baseline		
n	XX	
Mean (SD)	xx.x (xx.xx)	
Median	XX.X	
Min, Max	XX, XX	
Missing	xx	
Week 4		
N	XX	XX
Mean (SD)	xx.x (xx.xx)	xx.x (xx.xx)
Median	XX.X	XX.X
Min, Max	xx, xx	XX, XX
Missing	xx	XX
Week 12		
n	XX	XX
Mean (SD)	xx.x (xx.xx)	xx.x (xx.xx)
Median	XX.X	XX.X
Min, Max	xx, xx	xx, xx
• • • •		XX

Note(s): Baseline is defined as the Week 12 assessment from the previous study (NI-AC301 or NI-AC302). Source: Listing xx.x.x.x, Program: xxxxx.sas, Output: T\_xx.x\_x\_x\_xxxx.rtf, Generated on: DDMMMYYYY HH:MM

Programmer Note: Include all vital signs parameters (e.g. SBP, DBP, Pulse) and all available post-baseline visits. Missing not presented if no missing values.

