Previous Study	Subject ID	Visit	Date	Counter's Initials	Papules/Pustules	Nodules/Cyst:
rievieus seud i	542,555 12	11010	2400	111101010	rapares, rassares	reduites, equal
xxxxxx	xxxxxxx	Baseline	DDMMMYYYY	XXXX	XXX	XXX
		Week 4	DDMMMYYYY	XXXX	XXX	XXX
		Week 12	DDMMMYYYY	XXXX	XXX	XXX
		Week 24	DDMMMYYYY	XXXX	XXX	XXX
		Week 36	DDMMMYYYY	XXXX	XXX	XXX
		Week 40	DDMMMYYYY	XXXX	XXX	XXX
xxxxxx	xxxxxx	Baseline	DDMMMYYYY	XXXX	XXX	XXX
		Week 4	DDMMMYYYY	XXXX	XXX	XXX
		Week 12	DDMMMYYYY	XXXX	XXX	XXX
		Week 24	DDMMMYYYY	XXXX	XXX	XXX
		Week 36	DDMMMYYYY	XXXX	XXX	XXX
		Week 40	DDMMMYYYY	XXXX	XXX	XXX

Protocol Number: NI-AC303

Listing 16.2.7.3 Cutaneous Tolerability Safety Population

Previous Study	Subject ID	Visit	Date	Erythema	Scaling	Dryness	Pruritus	Burning/ Stinging
xxxxxxx	xxxxxxx	Baseline	DDMMMYYYY	Mild	Mild	Moderate	None	None
		Week 4	DDMMMYYYY	Mild	Mild	Moderate	None	None
		Week 12	DDMMMYYYY	Mild	Mild	Moderate	None	None
		Week 24	DDMMMYYYY	Mild	Mild	Moderate	None	None
		Week 36	DDMMMYYYY	Mild	Mild	Moderate	None	None
		Week 40	DDMMMYYYY	Mild	Mild	Moderate	None	None
xxxxxxx	xxxxxxx	Baseline	DDMMMYYYY	Mild	Mild	Moderate	None	None
		Week 4	DDMMMYYYY	Mild	Mild	Moderate	None	None
		Week 12	DDMMMYYYY	Mild	Mild	Moderate	None	None
		Week 24	DDMMMYYYY	Mild	Mild	Moderate	None	None
		Week 36	DDMMMYYYY	Mild	Mild	Moderate	None	None
		Week 40	DDMMMYYYY	Mild	Mild	Moderate	None	None

Note(s): 0 = None, 1 = Mild, 2=Moderate, 3 = Severe. s<nnn>xxxx yyyymmddthh:mm

Protocol Number: NI-AC303

Listing 16.2.7.4 Vital Signs Safety Population

Previous Study	Subject ID	Visit	Date/ Day	Systolic BP (mmHg)	Diastolic BP (mmHg)	Pulse (bpm)	Evaluation	If Abnormal and Clinically Significant, provide MH or AE term
xxxxxx	xxxxxx	Baseline	DDMMMYYYY/xx	xxx	xxx	XXX	Normal	
		Week 4	DDMMMYYYY/xx	XXX	XXX	XXX	Abnormal, NCS	
		Week 12	DDMMMYYYY/xx	XXX	XXX	XXX	Normal	
		Week 24	DDMMMYYYY/xx	XXX	XXX	XXX	Normal	
		Week 36	DDMMMYYYY/xx	XXX	XXX	XXX	Normal	
		Week 40	DDMMMYYYY/xx	XXX	XXX	xxx	Normal	
xxxxxxx	xxxxxxx	Baseline	DDMMMYYYY/xx	xxx	xxx	xxx	Abnormal, CS	xxxxxxxxxxx

Note(s): Day = Day relative to the first day of LTS. NCS = Not clinically significant; CS = Clinically Significant. If a post-baseline finding was determined to be clinically significant, it is also reported as an adverse event. s<nnn>xxxx yyyymmddthh:mm Novan Inc
Protocol Number: NI-AC303

Listing 16.2.7.5
Concomitant Medicati

Listing	16.2.7.5
Concomitant	: Medications
Safety F	opulation

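### Vital signs get only pooled descriptive statistics by visit: no output counts subjects with a marked blood-pressure or pulse change, although hypotension is a named theoretical risk

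*SAP*

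**What the plan says.** SAP 2.1 makes vital-sign change one of the study's safety endpoints: "Safety endpoints will include adverse events, changes in physical examination and changes in vital sign measurements". Protocol 1.5 explains why blood pressure is of interest: "theoretical risks from systemic exposure following topical administration of NVN1000 Gel or SB204 include hypotension and headache".

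SAP 4.5.4 provides for summaries of blood pressure and pulse at each visit, and states that "change from Baseline in vital signs will be summarized at Week 4, 12, 24, 36, and 40/ET". SAP 4.1 fixes the statistics: "Continuous data will be summarized with sample size (N), mean, median, standard deviation, minimum and maximum". The shell of Table 14.3.4 follows this, adds a row for missing values, and has a single SB204 column. Its programmer note reads "Include all vital signs parameters (e.g. SBP, DBP, Pulse) and all available post-baseline visits".

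Two other routes exist. Listing 16.2.7.4 shows each subject's systolic and diastolic pressure and pulse at each visit. It also shows an evaluation (normal, abnormal NCS or abnormal CS, where "NCS = Not clinically significant; CS = Clinically Significant") and any linked medical-history or adverse-event term. Protocol 4.3.3 adds: "Any clinically significant changes in vital signs from Baseline will be recorded as adverse events whether or not drug related". These events then enter the TEAE tables of SAP 4.5.1.

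**The concern.** If a topical nitric-oxide donor lowers blood pressure in practice, the effect may well be confined to a few subjects. A mean and median over about 600 people say little about a few. The usual safety output for this question is the number and percentage of subjects whose change passes a pre-set limit, and Table 14.3.4 has no such row. It has no worst post-baseline value per subject, and no table shows how the evaluation shifts from Baseline. The SAP does plan shift tables for the tolerability scores (Tables 14.3.2.1 to 14.3.2.5), so the format is already in use.

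At stake is how well the report can describe the size of any affected subgroup for one of the two systemic risks that the protocol itself names. Pooling adds a second difficulty, because change from Baseline does not mean the same thing in the two groups of subjects who enter.

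**Working it through.** **1. What each planned output can tell the reader**

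| Output | Gives | Does not give |
|---|---|---|
| Table 14.3.4 | n, mean (SD), median, min, max by visit, pooled | how many subjects changed markedly; worst value per subject; experienced/naïve split |
| Listing 16.2.7.4 | every value and evaluation; about 600 x 6 visits = 3,600 rows | any count or criterion |
| TEAE tables | subjects with changes judged clinically significant, under the reported term | changes judged not clinically significant |

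Neither document gives a numerical criterion for clinical significance. Protocol 7.9 plans about 600 subjects at about 100 sites, or about 6 per site. Protocol 8.3 confirms that the judgement is unblinded.

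**2. Baseline**

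Baseline is the Week 12 visit of the pivotal study (SAP 2; footnote to Table 14.3.4). SAP 3.5.1 separates subjects previously allocated to SB204 from those allocated to vehicle. The first group therefore has a Baseline after 12 weeks of SB204, applied to the face only (SAP 4.4). The second has a Baseline without SB204. Suppose SB204 shifts blood pressure early and by a constant amount D, whatever the area treated. Experienced subjects then show a change near 0 and naïve subjects a change near D. The pooled change is (1 - p) x D, where p is the experienced share. The documents do not give p, but any p above zero dilutes the effect.

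**3. Illustration**

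The plan has no figure to reproduce, since SAP 3.6 and Protocol 7.9 say that no sample size or power calculation was done. N = 600 is from Protocol 7.9. Everything else is assumed:
- Ordinary change in systolic pressure at one visit is normal, with mean 0 and SD s = 8, 10 or 12 mmHg.
- A fraction f has an extra fall d = 30 mmHg on top of that variation.
- The cut is a fall of 20 mmHg or more. It serves the arithmetic only and is not a proposed limit.

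Formulas:
- Mean shift = f x d. SE = s / sqrt(N), with s the ordinary SD.
- Background count = N x Phi(-20/s).
- Count with subgroup = N x [(1 - f) x Phi(-20/s) + f x Phi((d - 20)/s)].

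At f = 2% (12 subjects) and s = 10:
- Mean shift = 0.02 x 30 = 0.6 mmHg downward. SE = 10/24.5 = 0.41. Ratio = 1.5.
- Background count = 600 x 0.0228 = 13.7.
- With the subgroup: 588 x 0.0228 + 12 x 0.841 = 13.4 + 10.1 = 23.5.

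| s | f | Mean shift (SE units) | Background count | Count with subgroup |
|---|---|---|---|---|
| 8 | 2% | -0.6 (1.8) | 3.7 | 14.4 |
| 10 | 1% | -0.3 (0.7) | 13.7 | 18.6 |
| 10 | 2% | -0.6 (1.5) | 13.7 | 23.5 |
| 10 | 5% | -1.5 (3.7) | 13.7 | 38.2 |
| 12 | 2% | -0.6 (1.2) | 28.7 | 37.7 |

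The other columns of Table 14.3.4, at s = 10 and f = 2%:
- The SD moves from 10 to sqrt(100 + 0.02 x 0.98 x 900) = 10.8.
- The expected minimum change (by simulation) moves from about -31 to about -46 mmHg. With half as many affected (1%, 6 subjects) it is about -43. The minimum can flag a large individual fall but hardly separates 6 affected subjects from 12.

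**The case against.** The strongest reply is that the plan is coherent for a descriptive single-arm study. Table 14.3.4 reports the spread and the extremes, every value is listed with a clinical evaluation, and significant changes become adverse events that are counted by subject. All of this is true, and it rules out some readings that a reader might be tempted by:

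- That vital signs are analysed only as means. They are not: median, SD, minimum and maximum are planned, with a subject listing.
- That an affected subgroup would go unseen. The documents do not support this. The minimum would probably move, the falls would stand in Listing 16.2.7.4, and those judged significant would be in the TEAE tables. What is missing is a planned count.
- That a threshold count would equal the number affected. It would not: ordinary variation also crosses any limit, as the background column shows.
- That the physical examination needs the same treatment. SAP 4.5.3 says "The results of the physical exams will be presented in a listing", but clinically significant changes also become adverse events. The examination is done only at Baseline and Week 40/ET and has no stated link to hypotension. A shift table there would add little.

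Three further points stand as limits on the remedy. There is no concurrent vehicle arm. Drug is applied at home before bedtime (Protocol 3.4 and 4.1), while pressure is taken at clinic visits, so a short-lived effect after application may be missed by any table. The risk is also described as theoretical: Protocol 1.5 reports no detectable systemic exposure to NVN1000 and no change in plasma nitrate. These points lower the urgency. They do not explain why data already collected on a named endpoint should go uncounted.

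**Conclusion.** The point holds as a gap in the planned outputs. No output gives the number of subjects with a marked change in blood pressure or pulse, none tabulates the collected evaluation, and Table 14.3.4 pools subjects with on-drug and off-drug Baselines. The size of a small affected subgroup would have to be inferred from the minimum, from reading the listing, and from adverse events resting on an undefined judgement.

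Under the assumed SD of 10 mmHg, a 2% subgroup moves the mean by 1.5 standard errors, while the count with a fall of 20 mmHg or more goes from about 14 to about 24. The excess is about 9 to 11 subjects over SD 8 to 12. The background itself runs from about 4 to about 29 over that range, so a count describes the subgroup better than the mean does but does not by itself prove a drug effect. At 5% affected, the mean alone would move by 3.7 standard errors, so the concern is about small subgroups. The SD, the affected fraction, the size of fall and the normal model are all assumptions. The lack of a count and the pooled column can be read directly from the SAP. The change is worth making but is not critical to the study.

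**What to change.** In SAP 4.5.4 and Table 14.3.4:

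- Add n (%) of subjects whose systolic pressure, diastolic pressure or pulse change from Baseline crosses pre-set limits, at each visit and at the worst post-baseline value. The sponsor's medical monitor should set the limits before database lock and the SAP should record them.
- Add a shift table of the normal / abnormal NCS / abnormal CS evaluation from Baseline to post-baseline.
- Present both, and the existing statistics, in SB204 Experienced / SB204 Naïve / Overall columns, as Table 14.3.3.1 already does for TEAEs.
- State in a footnote that Baseline follows SB204 treatment for experienced subjects and vehicle for naïve subjects.

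The cost is SAP wording and one or two extra tables from data already collected, with no new assessment. The downside is interpretive: the counts need reading against background variability. The worst-value count will have a higher background than the single-visit figures above, because each subject has up to five chances to cross a limit. The report should say that there is no vehicle comparison and that clinic readings are not timed to the bedtime application.

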#### 4.5.5 Urine Pregnancy Tests

Urine pregnancy tests results for WOCBP will be presented in data listings by subject.

### 4.6 Tolerability

Distribution and shift in cutaneous tolerability assessments (erythema, scaling, dryness, pruritus, burning/stinging) will be summarized from Baseline to Week 40/ET.

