3. STUDY DESIGN

Figure 1 depicts the overall study design for this 40-week, open label study in subjects with acne vulgaris dosed once daily with SB204 4%. Subjects must have completed participation in one of the pivotal acne trials (NI-AC301 or NI-AC302) to be eligible to participate in this long term safety trial. Subjects will be treated chronically or repeatedly as recommended by the Investigator for up to 40 weeks. The Investigator may stop treatment if the subject's acne is in remission and re-initiate treatment if the subject's acne recurs. Any subject who is determined to be clear will remain enrolled in the study until study completion or termination. The total time on study will be counted as the days from enrollment until the subject discontinues or the study terminates.

Figure 1: Study Diagram

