3.6 STUDY POPULATION

Approximately 600 healthy male and female subjects with acne vulgaris on the face, chest, shoulders or back will be allowed to participate in the study if they have successfully completed 12 weeks in either NI-AC301 or NI-AC302.

A subject whose facial acne cleared during NI-AC301 or NI-AC302 is eligible to enroll if all other inclusion criteria and none of the exclusion criteria are met. If a subject enters the pivotal study at age 40 and is 41 at the time they complete participation in the pivotal study, they are eligible for the long term safety study as long as they meet all other study inclusion criteria and none of the exclusion criteria.

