4.1.2 WEEKS 4, 12, 24 AND 36 (DAYS 28, 84, 168, 252)

The following procedures must be performed and recorded at the Weeks 4, 12, 24, and 36 visits:

- 1. Update concomitant medication information.
- 2. Update AE information and record any new AEs if applicable.
- 3. Obtain UPT (WOCBP only) and evaluate results.
- 4. Collect blood pressure and pulse rate after the subject has been sitting quietly for 5 minutes.

- 5. Perform cutaneous tolerability evaluation (face only).
- 6. Perform lesion counts (face only).
- 7. Record areas treated since last visit (face, upper back, upper chest/shoulders).
- 8. Collect returned study drug and diary, perform accountability, and review study drug compliance with subject.
- 9. Review subject diary for completion.
- 10. Dispense new study drug and diary.
- 11. Review and confirm the study schedule with the subject.

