4.2 TOLERABILITY ASSESSMENTS

The evaluator will assess the subject's face at baseline and each study visit. The cutaneous tolerability scores from Week 12 of NI-AC301 or NI-AC302 will be the subject's baseline tolerability. The cutaneous tolerability assessment should be performed at least 30 minutes after study drug application. Cutaneous tolerability evaluations will include erythema, scaling, dryness, pruritus and burning/stinging. Pruritus and burning/stinging will be based on the subject's report for the previous 24 hours. Cutaneous tolerability endpoints will not be reported as an AE unless they reach severe and/or result in subject's discontinuation from the study. Subjects who develop intolerance to the product as defined by scores of 3 (severe) on two or more categories of tolerability (erythema, scaling, dryness, pruritus, burning/stinging) shall be discontinued from the study. Cutaneous tolerability assessments will be performed according to the following scales:

Erythema

Score Description

0-None No evidence of erythema present

1-Mild Slight pink coloration

2-Moderate Definite redness

3-Severe Marked erythema, bright red to dusky dark red in color

Scaling

ScoreDescription0-NoneNo scaling

1-Mild Fine scales present to limited areas of the face, barely perceptible

2-Moderate Fine scale generalized to all areas of the face

3-Severe Scaling and peeling of skin over all areas of the face

Dryness

ScoreDescription0-NoneNo dryness

1-Mild Slight but definite roughness

2-Moderate Moderate roughness 3-Severe Marked roughness

Pruritus

Score Description
0-None No itching

1-Mild Slight itching, not very bothersome

2-Moderate Moderate amount of itching, somewhat bothersome

3-Severe Severe amount of itching, definite discomfort and sleep may be disturbed

Burning/Stinging

Score Description

0-None No burning/stinging

1-Mild Slight warm, burning/stinging sensation; not very bothersome

2-Moderate Definite warm, burning/stinging sensation that is somewhat bothersome

3-Severe Hot, tingling/sensation that has caused definite discomfort and may have

disturbed sleep

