# 3 Study Design

### 3.1 Study Design

This is a multi-center, open label long-term safety (LTS) study to be conducted in approximately 600 subjects with acne vulgaris. Subjects will be enrolled into the study from approximately 100

sites in North America. Subjects eligible to enroll in this study will have completed one of the Phase 3 pivotal studies with SB204, NI-AC301 or NI-AC302, and meet study inclusion and exclusion criteria.

Subjects who satisfy the entry criteria at the Baseline visit will be enrolled to receive open-label SB204. Investigational drug will be delivered from a double barrel single pump dispenser. The pump dispenses product (NVN1000 Gel and a hydrogel) from two chambers which will be mixed together quickly (about 5 seconds) by the subject and applied once daily to the acne affected areas identified by the Investigator. Areas that could be treated include the face, upper chest, upper back and shoulders. No other acne treatments will be permitted during the study.

Subjects will return for post-baseline evaluation at Weeks 4, 12, 24, 36 and 40/ET.

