### Programming Note: Repeat table for Non-Inflammatory Lesions:

Table 14.2.3.2 Non-Inflammatory Lesion Counts (Face Only) by Prior Treatment and Study Visit Safety Population

Protocol Number: NI-AC303

Table 14.3.1.1

Cutaneous Tolerability Evaluation - Erythema - Summarized by Study Visit (Face Only)

Safety Population

	SB204
Study Visit	(N=XXX)
Baseline	
0 - None	xx (xx.x)
1 - Mild	xx (xx.x)
2 - Moderate	xx (xx.x)
3 - Severe	xx (xx.x)
Missing	xx (xx.x)
Week 4	
0 - None	xx (xx.x)
1 - Mild	xx (xx.x)
2 - Moderate	xx (xx.x)
3 - Severe	xx (xx.x)
Missing	xx (xx.x)
Week 12	
0 - None	xx (xx.x)
1 - Mild	xx (xx.x)
2 - Moderate	xx (xx.x)
3 - Severe	xx (xx.x)
Missing	xx (xx.x)
Week 24	
0 - None	xx (xx.x)
1 - Mild	xx (xx.x)
2 - Moderate	xx (xx.x)
3 - Severe	xx (xx.x)
Missing	xx (xx.x)
Week 36	
0 - None	xx (xx.x)
1 - Mild	xx (xx.x)
2 - Moderate	xx (xx.x)
3 - Severe	xx (xx.x)
Missing	xx (xx.x)
Week 40\ET	
0 - None	xx (xx.x)
1 - Mild	xx (xx.x)
2 - Moderate	xx (xx.x)
3 - Severe	xx (xx.x)
Missing	xx (xx.x)

Note: Baseline is the Week 12 assessment from the previous study (NI-AC301 or NI-AC302).

Source: Listing xx.x.x.x, Program: xxxxx.sas, Output: T\_xx.x\_x\_x\_xxxx.rtf, Generated on: DDMMMYYYY HH:MM

Protocol Number: NI-AC303

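### The facial tolerability tables pool treated and untreated faces; add a by-visit count and split by facial treatment so that tolerability on treated skin can be read

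*SAP*

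**What the plan says.** **The analysis.** SAP 4.6: "Distribution and shift in cutaneous tolerability assessments (erythema, scaling, dryness, pruritus, burning/stinging) will be summarized from Baseline to Week 40/ET". The shells carry this out for the Safety Population. Table 14.3.1.1 is titled "Cutaneous Tolerability Evaluation - Erythema - Summarized by Study Visit (Face Only") and has one SB204 column, with rows for scores 0 to 3 and Missing at each visit. Tables 14.3.1.2 to 14.3.1.5 repeat it for the other signs, and Tables 14.3.2.1 to 14.3.2.5 cross-tabulate each visit against Baseline. The safety population is everyone with at least one dose of SB204 (SAP 3.5.1), to whatever area, and percentages are based on N (SAP 4.1).

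**The assessment.** Protocol 4.2: "The evaluator will assess the subject's face at baseline and each study visit". Protocol 4.1.2 has sites "Perform cutaneous tolerability evaluation (face only"), and 4.1.3 repeats this at Week 40/ET. Neither makes scoring depend on facial treatment.

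**Where the drug goes.** In SAP 3.1 it is "applied once daily to the acne affected areas identified by the Investigator", and the face is listed there as one of the areas that could be treated. Protocol 3.6 admits acne on the face, chest, shoulders or back, and adds: "A subject whose facial acne cleared during NI-AC301 or NI-AC302 is eligible to enroll". Protocol 3: "The Investigator may stop treatment if the subject's acne is in remission and re-initiate treatment if the subject's acne recurs". It also keeps a clear subject enrolled.

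**What is recorded.** Protocol 4.1.2 has sites "Record areas treated since last visit (face, upper back, upper chest/shoulders"), and Week 40/ET does the same. The only planned summary table of areas, Table 14.2.1, shows whether each area was ever treated, not facial use by visit.

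**The concern.** A score from a face that received no drug in the interval enters the same cell as a score from a treated face. The Missing row does not separate them, because an untreated face still has a score. The subject-reported items raise the same difficulty: pruritus and burning/stinging cover the previous 24 hours, which for such a subject is a period without facial drug. Protocol 4.2 also times scoring at least 30 minutes after application, which presupposes use.

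What is at stake is how well SB204 is tolerated on the skin where it is applied. Under Protocol 4.2 these signs become adverse events only if they reach severe or lead to discontinuation. Mild and moderate reactions are therefore summarised in the tolerability displays and not in the adverse event tables. The SAP relates adverse events to duration and extent of exposure, but gives tolerability no such link.

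The shift tables have a related difficulty. SAP 4.4 states that in the pivotal studies drug went to the face only, so Baseline for an SB204-experienced subject is a facial score taken after SB204 treatment. If that subject later stops treating the face and a sign resolves, the table shows an improvement on SB204. The shift shells do not separate experienced from naïve subjects.

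**Working it through.** The documents state no tolerability rate, no expected share of untreated faces and no sample-size calculation, so there is no plan figure to reproduce. The check is first of structure, then of direction and possible size.

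**Step 1: can a scored face be untreated?** There are three routes.

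1. At entry: facial acne already cleared, with acne elsewhere (Protocol 3.6).
2. By choice of area: the investigator's affected areas need not include the face (SAP 3.1). Protocol 7.7 likewise joins the areas with and/or.
3. During the study: treatment stopped in remission, with the subject still enrolled (Protocol 3) and still scored (Protocol 4.1.2 and 4.2).

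Neither SAP 4.6 nor the shells restrict or split by facial treatment.

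**Step 2: what does the table estimate?** At one visit, let u be the share of scored subjects whose face was untreated in the interval, and let p_treated and p_untreated be the rates of a given sign. Then

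tabulated rate = (1 − u) × p_treated + u × p_untreated.

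The difference from p_treated is u × (p_untreated − p_treated). It is zero if u = 0 or the rates are equal, negative if untreated faces show fewer signs, and positive if they show more.

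**Step 3: illustration.** All inputs are assumptions. With p_treated = 20%:

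| u | p_untreated 0% | 5% | 10% | 20% |
|---|---|---|---|---|
| 10% | 18.0% | 18.5% | 19.0% | 20.0% |
| 20% | 16.0% | 17.0% | 18.0% | 20.0% |
| 30% | 14.0% | 15.5% | 17.0% | 20.0% |
| 40% | 12.0% | 14.0% | 16.0% | 20.0% |

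For example, 0.8 × 20% + 0.2 × 10% = 18%. With p_treated = 10%, p_untreated = 5% and u = 20%, the table shows 0.8 × 10% + 0.2 × 5% = 9.0%. In the opposite direction, p_treated = 5%, p_untreated = 10% and u = 20% gives 6.0%.

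**Step 4: shift tables.** The same identity applies within each Baseline score. The share moving to a lower score is a weighted mean of the shares among those who still treat the face and those who do not. If signs resolve more often off drug, the pooled shift looks more favourable than the shift on treated skin.

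**Step 5: what the split costs in numbers.** If all of the approximately 600 planned subjects were scored, u = 10%, 20% or 30% would leave 540, 480 or 420 treated faces and 60, 120 or 180 untreated ones.

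**The case against.** The strongest reply is that the all-subject table is a legitimate summary. Protocol 3 describes chronic or repeated treatment with pauses, and tolerability in everyone dosed under that regimen is a valid descriptive quantity. The study has no test, margin or decision rule. This stands, and is why the all-subject table should stay.

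Second, untreated faces are permitted but not shown to be common. A reader might infer from the separate Face row in Table 14.2.1, or the marks in the mock Listing 16.2.6, that the sponsor expects them. Neither supports that: one is a checklist row and the other holds placeholders. Other text leans towards facial use, such as the pump stroke assigned to the face in Protocol 3.4 and the worked exposure examples in SAP 4.4, all of which include the face. This bears on size, not structure.

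Third, a reader might infer that every rate is diluted by the factor 1 − u. That requires untreated faces always to score 0. The scales record signs whatever their cause, so some background erythema or dryness off drug is plausible. Protocol 1.5 associates erythema, scaling, dryness and burning/stinging with application, which makes a lower untreated rate plausible, but the documents do not quantify it.

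Fourth, restricting the main table to treated faces could bias it the other way. A subject who stops facial use because of irritation would drop out of that table from the next interval. This also stands.

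Last, the link is partly traceable: Listing 16.2.6 gives areas by visit and Listing 16.2.7.3 gives scores by visit. A reader could join them by subject, but no planned summary does so.

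**Conclusion.** The concern holds as a matter of structure. The tolerability tables mix treated and untreated faces, and no planned summary shows the mix by visit. If untreated faces show fewer signs, the tables understate reactions on treated skin, and stopping facial use can appear as improvement in the shift tables.

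The size cannot be stated: u, p_treated and p_untreated are all absent from the documents. Over the illustrative range, a 20% rate on treated faces is tabulated anywhere from 12% to 20%; the effect may be negligible.

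It is also tempting to conclude that u grows as faces clear, so that the tables would show a false improvement with long-term use. Pauses in remission make this possible, but nothing in the documents establishes it, and recurrence with re-treatment works the other way. The by-visit count would settle it.

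This is a cheap improvement to a descriptive endpoint. It does not make the planned tables wrong for the population they describe.

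**What to change.** In SAP 4.6 and shells 14.3.1.x and 14.3.2.x:

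- Keep the all-subject tables as planned.
- For each post-baseline visit, classify a subject as treating the face if the areas recorded since the last visit include the face and there is at least one reported application day in the interval; otherwise as not treating it. Count subjects with unknown use separately, since Listing 16.2.6 already provides for unknown exposure.
- Report the number in each group at each visit, and show the score distribution and the shift from Baseline separately for each group.

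The change is to SAP and shell wording and to programming; no new data or procedure is needed.

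The SAP should state three downsides:

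- **Smaller denominators** in each group.
- **Interval, not day.** Areas are recorded over intervals of up to 12 weeks (Week 12 to 24 and Week 24 to 36). A subject who treated the face early and then stopped still counts as treating it. The documents do not say that the diary records applications by area, so the mismatch with the 24-hour items is reduced, not removed.
- **Selection.** Facial use after Baseline may depend on irritation, so the treated-face group can look better than experience in all who started. The all-subject table should therefore be read alongside it.
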